4.0 REGISTRATION PROCEDURES

Patient Recruitment and Consent

Based on our R34 enrollment pace (43 romantic partner couples over 3 months of recruitment), we estimate a recruitment rate of 14–20 dyads per month across 12 months. We anticipate a faster recruitment pace for the proposed study than the R34 because of expansion of inclusion criterion from romantic partner to any family member. The majority of AUD outpatients have at least one family member78; in one large study of AUD outpatients, 86% had a family member or significant other willing to participate in baseline and follow-up assessments.79 Recruitment pace may also increase because data plans will be provided. Finally, there is no need to visit a clinic, and phones can be delivered to homes, a process we have successfully used in the past.

After we receive initial indication of interest, we will call the dyad to describe the study. CHESS staff will speak with each member of the dyad individually and follow the phone screening script to determine eligibility. If only one member of the dyad is available, we will ask for permission to send the other member a letter, or an email or text, with a link to the letter. The letter contains a description of the study and how to contact CHESS staff if interested.

If the drinker and partner are eligible and interested, we will go through the informed consent individually on the phone. Since all recruitment will be done remotely, we will

be collecting verbal consents. A Partial waiver of HIPAA authorization to not require signature of the individual and date (e.g. verbal) will be submitted to UW's IRB, based on the following:

- The use or disclosure of protected health information involves no more than a minimal risk to the privacy of individuals, based on, at least, the presence of the following elements: (Check if "Yes". All must be checked)
 - An adequate plan to protect the identifiers from improper use and disclosure.

The consent process will inform potential subjects of:

- (1) the nature and purpose of the study
- (2) the types of data that will be collected from FAM-CHESS-C and ACHESS
- (3) study risks and measures taken to mitigate
- (4) their right to leave the study at any time
- (5) the timeline of the study

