AIM 1: FamCHESS-C Refinement (Months 1–6). Aim 1 is to modify PartnerCHESS in 3 fundamental ways to create FamCHESS-C: 1) Add COVID material already in ACHESS-C, information on vaccines, long-term effects of COVID, and heightened risk from AUD/SUD. 2) Expand PartnerCHESS from focus on romantic partner to any family member. 3) Added content targeting comorbid drug use (psychoeducation, tools to stop, tools for partner to help, and psychoeducation on relationship of drugs to COVID risk and sequelae). Our software design team will recruit 10 dyads for evaluation to assure that we offer appropriate content and delivery in the proper style. The 10 dyads will be recruited from colleagues with lived experience and their personal networks. All refinements will employ rapid cycle testing, refining, and retesting based on feedback from the 10 dyads about difficulties and benefits. Both members of the dyad will engage in think-aloud protocol to assess their in-the-moment reactions as they use the app prototype. Throughout the month of pilot use, dyads will be asked about the extent to which the language, presentation style, and structure are understandable, engaging, intuitive, and relevant to their experience. We will use wireframes, mockups, and html to test prototypes, use feedback to quickly make changes, and test again. We will continue to improve FamCHESS-C throughout the adaptation and pilot phase. Our strategy is based on Shewhart's Plan, Do, Check, Act cycle.²⁹ Refinements to baseline and followup surveys will also be tested with the dyads.

AIM 2: Conduct an RCT to Test Smartphone Control vs. ACHESS-C vs. FamCHESS-C (Months 7-30).

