7.0 STUDY PARAMETERS

198 dyads will be recruited, 66 in each of 3 conditions to yield approximately 180 dyads at 8-month analysis.

They will be allowed to keep the phone, so that they could continue to use those interventions if they had other ways to access the two systems. Partners in the A-CHESS group will not have access to either app.

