Qualitative Analyses (Aim 4). Transcripts of qualitative interviews concerning perceived difficulties and benefits of app use will be examined using Braun and Clarke's¹⁰² six-phase procedure for thematic analysis: 1) familiarization with data, 2) generation of initial codes, 3) identifying instances of themes, 4) review of themes, 5) defining and naming themes, 6) production of findings. To improve consistency and accuracy, coders will work separately using NVivo software; findings will be compared and discussed until consensus is reached.

Interim Analyses and Stopping Plan. The interim analyses are solely to check whether the stopping plan needs to be implemented. They will not be reported as tests of our hypotheses and thus will not inflate Type 1 error. We will engage in the following practices: 1) We will report any fatalities as they occur, as required by the university IRB. 2) Our statistician will conduct interim analyses at months 18 and 27 after the start of the study (9 and 18 months after recruiting begins), examining our primary outcome of substance use days in the two arms. She will share the results with UW's independent Data Safety and Monitoring Board but not with the Pls unless instructed to do so by the Board. Because all of our prior research has been designated low-risk by

the IRB, we anticipate the same designation in this case. Barring exceptional disparities in outcomes between conditions, we do not anticipate stopping the trial. As an *a priori* rule, we believe we should stop if our primary outcome of functional health shows a T-score difference greater than 6 (averaged across components of the PROMIS-29). A T-score of 6 is at the very upper end of the clinically meaningful differences for PROMIS-29 components (e.g. physical function, pain, fatigue).^{22,30} We have no reason to anticipate such an occurrence. We will follow Data Safety Monitoring Board guidance on this matter.

Missing Data. In previous RCTs, we completed about 85% of interviews through 12 months and kept missing data on core interview items to about 2%. We expect these rates in this study. We will identify missing data patterns and use pattern-mixture modeling to test the sensitivity of our analysis to missing data assumptions.¹⁰³⁻¹⁰⁶ We will conduct other sensitivity analyses after imputing missing data with a range of plausible values based on assumptions for the missing data (e.g. best-case, worst-case; with and without multiple imputation).¹⁰⁷⁻¹⁰⁹

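### The only numeric stopping rule makes no allowance for sampling error, so at the first look arms that do not differ could cross it by chance if month-8 data are used

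*Combined protocol and SAP*

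**What the plan says.** The interim paragraph of section 8.0 schedules two looks, at study months 18 and 27, described as "9 and 18 months after recruiting begins". Its a priori rule is: "we believe we should stop if our primary outcome of functional health shows a T-score difference greater than 6", where the score is "averaged across components of the PROMIS-29". The reason given for the threshold is that "A T-score of 6 is at the very upper end of the clinically meaningful differences for PROMIS-29 components". The paragraph adds that the authors do not expect a crossing and that they will take the monitoring board's guidance.

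Neither that paragraph nor the monitoring committee text in section 10.0 gives a standard error, confidence interval, p-value, boundary or minimum number of dyads for the rule. The visit, the pair of arms and the direction of the difference are also left open.

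On accrual, section 4.0 says "we estimate a recruitment rate of 14–20 dyads per month across 12 months". On size, section 7.0 says "198 dyads will be recruited, 66 in each of 3 conditions to yield approximately 180 dyads at 8-month analysis". Surveys are at baseline and months 4, 8 and 12 (section 5.0).

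**The concern.** A clinical-importance threshold says how large a true difference would have to be to matter. It does not say whether an observed difference can be told apart from noise. When few dyads have reached the visit used, the standard error of the difference can be as large as the threshold, and a 6-point gap between identical arms is then unremarkable.

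This is the plan's only numeric stopping rule. Applied as written, it could put a stop recommendation before the board on the strength of a quality-of-life fluctuation in 14–20 dyads. The trial is sized on percent heavy drinking days and needs 198 dyads to answer that question.

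**Working it through.** **The plan's own figures.** No false-stop probability is stated, so there is none to reproduce. The accrual figures agree with each other: 198 / 12 = 16.5 dyads per month, inside the stated 14–20, and 198 / 3 = 66 per arm.

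**Inputs from the documents.** Threshold 6; looks at 9 and 18 months of recruiting; 14–20 dyads per month; 198 dyads in three equal arms; visits at months 4 and 8.

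**Assumptions.** The SD of the averaged T-score is not given. I take 10 for a single T-score and a range of 5, 7.5 and 10 for the composite. Averaging imperfectly correlated components lowers the SD, and so does averaging the two members of a dyad. The true difference is 0, estimates are normal, and survey completion is full unless stated.

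**Formulas.**
- Dyads per arm with data: n = min(198, rate × (look − visit)) / 3.
- Standard error of a difference: SE = SD × √(2/n).
- One pair: P = 2 × (1 − Φ(6/SE)).
- Any of three pairs: the probability that the range of three simulated arm means exceeds 6.

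**First look, month-8 data.** n = 14 × (9 − 8) / 3 = 4.67 to 20 × 1 / 3 = 6.67.
- Highest risk: SD 10, n = 4.67. SE = 10 × √(2/4.67) = 6.55; 6/6.55 = 0.92; P = 36%.
- Lowest risk: SD 5, n = 6.67. SE = 5 × √(2/6.67) = 2.74; 6/2.74 = 2.19; P = 3%.

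**All cases** (each cell: one pair; any of three pairs)

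| Data used | n per arm | SD 5 | SD 7.5 | SD 10 |
|---|---|---|---|---|
| Look at 9 months, month-8 data | 4.7–6.7 | 3–7%; 7–16% | 14–22%; 31–44% | 27–36%; 52–63% |
| Look at 9 months, month-4 data | 23–33 | about 0; about 0 | 0.1–0.6%; 0.3–1.8% | 1.4–4.0%; 4–10% |
| Look at 18 months, month-8 data | 47–66 | about 0; about 0 | about 0; below 0.1% | 0.1–0.4%; 0.2–1.1% |
| Look at 12 months, month-8 data | 19–27 | about 0; below 0.1% | 0.4–1.5%; 1–4% | 3–7%; 7–16% |

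The last row is there because section 5.0 places the trial in study months 7–30. If recruiting starts after month 6, the month-18 look falls about 12 months into recruiting, not 9. The two timings need reconciling.

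**Survey completion.** Section 8.0 expects about 85% of interviews. At 14 dyads per month this gives 14 × 0.85 / 3 = 4.0 per arm with month-8 data at the first look, and the SD 10 figures rise to 40% and 67%. With month-4 data, n = 70 × 0.85 / 3 = 19.8, and they rise to 6% and 14%.

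**Where 6 points stops being noise.** For 6 to equal 1.96 SE, n = 2 × (1.96 × SD / 6)², which rounds up to 6, 13 or 22 per arm at SD 5, 7.5 or 10. The first look with month-8 data is at or below that range, and the second look is well above it.

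**The case against.** The strongest reply is that the headline risk needs several things the plan does not state. The rule names no visit. The planned mixed model uses successive observations, so month-4 data need not be discarded at the first look, and with them the risk is small. If the two dyad members' scores are averaged, the SD moves towards the low end of the range. If the look falls 12 months into recruiting, the one-pair risk is at most about 7%. All of this stands, and it limits the size of the point. It does not remove it: nothing in the documents excludes month-8 data, which is the visit the sample size refers to, and none of these readings supplies a precision condition.

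A second reply is that the board decides. The rule is worded as a belief, the board's guidance is to be followed, and the interim also examines substance use. A board shown five dyads per arm can discount the result. That also stands, so the crossing probabilities are not probabilities of stopping. Even so, the board is handed an a priori rule with no indication of how often chance would trigger it.

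A reader might infer three stronger things. The first is a high false-stop rate throughout; the second look contradicts that. The second is an automatic stop; the deference to the board contradicts that. The third is an inflated Type 1 error in the final analysis. That does not follow either, because the issue here is a mistaken recommendation to stop, not a false claim of benefit.

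**Conclusion.** The point holds in a limited form. The stopping rule compares an estimate with a clinical threshold and ignores sampling error. The consequence is material in one situation: the first look, 9 months into recruiting, judged on month-8 data from about 5–7 dyads per arm. There the chance crossing for identical arms is about 3–36% for one pair and 7–63% for any of three pairs. In the other cases, with full survey completion, the upper bounds for one pair are about 4% (month-4 data at the same look), 0.4% (second look) and 7% (first look at 12 months).

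The ranges rest on an assumed composite SD of 5–10 and the stated accrual. The absence of a precision condition rests on the text alone.

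**What to change.** Add one sentence to the interim paragraph of section 8.0: the rule is met only if the estimated difference exceeds 6 and its confidence interval, at a stringent level fixed in advance, excludes 0. A 99.9% interval of Haybittle-Peto type would serve. Require that the estimate go to the board with its interval and the number of dyads per arm, and keep the rule advisory. Use a t-based interval, since a normal one is too narrow at 5–7 per arm.

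Chance crossings then stay at about 0.1% per pair per look, and at most 3 × 0.1% = 0.3% for any of three pairs at one look.

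The cost is that a true large difference, including a harmful one, needs more data before the rule fires. Using 3.29 × SE as a guide at SD 7.5, the difference needed at the first look with month-8 data is about 3.29 × 4.11 = 13.5 to 3.29 × 4.91 = 16.2 points. At the second look it is 3.29 × 1.31 = 4.3 to 3.29 × 1.55 = 5.1, so the 6-point threshold still governs. The board can act on its own judgement in the meantime.

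A fixed minimum such as 30 dyads per arm is not advised. The first look has only 5–7 per arm at month 8 and 23–33 at month 4, so a floor of that size would largely disable it. No visit, treatment or sample size changes.

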Data collection. Surveys will be conducted with both members of the dyad in all three study arms every 4 months (baseline, 4, 8, and 12 months). Each participant receives \$25 per completed survey. Payments will be processed in 2 ways. If the participant prefers to receive the payment in the mail, we will send cash to the participant within 5 business days of their survey being completed. If the participant prefers to receive payment through a mobile app, we will send them payment through Venmo or Paypal.

UW staff blind to the hypotheses will conduct the surveys. To ensure fidelity and data quality, we will record interviews, and [name] will review a subset and provide feedback. All uses of the apps are automatically logged to create measures of use of different services. Survey data will be double-entered into ICTR REDCap and compared to reduce the chance of data-entry errors. Both survey and app data are stored on a UW Division of Information Technology HIPAA-secure server using the Campus Computing Infrastructure. The timing of interviews will be based on enrollment date.

Once the trial begins, we will analyze app use data every 2 weeks to note trends in services used most and differences in use patterns between drinkers and partners. One tool for drinkers in ACHESS-C and FamCHESS-C will be a weekly survey adapted from the Brief Alcohol Monitor (BAM),81 with four COVID-related protective behavior questions added. Our adaptation of the BAM asks about 5 factors that put patients at risk of relapse and 5 factors that protect. Responses help CHESS systems tailor services to individual patients and partners. We will also add questions to the every-4-months interviews. Some app-based questions will change over time as we explore specific issues. For instance, if a service is not used for a month, we will add a question about why. If certain services are used a great deal, we will ask how and why it's useful, to understand if additional related resources are needed.

Keeping patients and partners engaged. Other CHESS studies have increased engagement in 4 ways. We will use all: 1) Monitor and respond to changes in the amount of app use. 2) Examine discussion posts using tools we developed that are based on Linguistic Inquiry and Word Count74 and machine learning82-84 to

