automatically predict relapse and intervene (e.g. an alert sent to a counselor). 3) Use ecological momentary assessments and weekly check-in data to identify and act on disconcerting trends (e.g. call to ask how the person is doing; refer users to relevant app services, games, and customized tips to address concerns, e.g. sleep). 4) Like other content-based or social media apps (e.g. NYT.com, FaceBook), relevant new information, resources, and user-generated content across the range of app topics, including alcohol use, couple skills, and COVID-19, is continuously added so that people keep coming back.

If drinkers stop using the app. We will be automatically notified of drinker non-use lasting 2 weeks. The project director will then make contact to resolve problems and encourage use. Those not using their app will still be included in the post-test interviews to understand reasons for stopping.

Dissolution of the relationship. If a family partner and drinker separate, we will encourage both to continue the study. At either's request, we will disengage portions of FamCHESS-C connecting them to each other. If one wishes to quit, we will honor their choice but encourage them to continue answering surveys.

Qualitative interviews. We will conduct qualitative interviews with a subset of participants who were randomized into the FamCHESS arm. Interview questions were developed by the study investigators to fill in the gaps where quantitative data alone may fall short. For example, how they decided to join the study, did they use the app together, did the app spark specific behavior change techniques. We will contact participants by phone or email to see if they are interested in taking part in a 45-minute qualitative phone interview. We will try to reach participants a maximum of three times. This is the script for leaving a voicemail:

"Hi. This is <name of study staff> from the UW Partner Study. I'm checking to see if you'd be interested in doing a phone interview with us so we could learn about your experience using the PartnerCHESS app. It will take about 45 minutes, and we would compensate you \$20 for taking part. Call or text if you're interested in finding out more. I'll also send you an email message to see if you're interested. Thanks!"

This is the script for leaving an email message:

Subject Line: UW Interview Opportunity

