"Hi. This is <name of study staff> from the UW Partner Study. I'm checking to see if you'd be interested in doing a phone interview with us so we could learn about your experience using the PartnerCHESS app. It will take about 45 minutes, and we would compensate you \$20 for taking part. If you're interested, email us back or you can call me at <study staff work phone number>."

We will explain that the interview is voluntary, and they can refuse if not interested. Participants will be paid \$20 for completing the interview. To cover a wide range of

experiences with the app, we will look at app use data to find a pool of potential interviewees. Our goal is to interview participants across the spectrum of app use, from very little to very much. Recruitment will continue until thematic saturation has been reached. We define thematic saturation as the point at which additional data lead to no new themes, when the researcher is empirically confident having repeatedly seen similar instances of data, and themes (or patterns in the data) are well-developed with diminishing returns from further data collection. If a participant agrees to the interview but does not want to be audio recorded, we will continue the interview, taking handwritten notes.

Audio recordings will be saved to HIPAA compliant servers managed by UW-Madison's College of Engineering Computer Aided Engineering with restricted access to CHESS study staff. Study staff will create de-identified transcripts for review by researchers. 7 years after study completion, all audio recordings will be destroyed.

Descriptions of the 3 Study Arms.

Summary of smartphone control arm. Both the drinker and family partner will receive a smartphone with pre-programmed contact information for Alcoholics Anonymous (AA), Narcotics Anonymous (NA), Al-Anon, Adult Children of Alcoholics (ACOA), and crisis hot lines.

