Summary of ACHESS-C and FamCHESS-C arms. In ACHESS-C, both the drinker and the partner will receive a smartphone, but only the drinker will receive the ACHESS-C app. The partner will receive a smartphone with contact information for standard AUD, SUD, and crisis support. In the FamCHESS-C arm, drinker and partner will both receive a smartphone with the FamCHESS-C app, which contains ACHESS-C services plus ABCT/ PartnerCHESS services. As described below, both the ACHESS-C and FamCHESS-C apps will contain services designed to address relapse factors of lifestyle imbalance, desire for indulgence, urges and cravings, high-risk situations, low selfefficacy, lack of coping responses, previous lapses, and abstinence violations.

ACHESS-C services. ACHESS-C offers the following, which are also available in FamCHESS-C:

COVID content. COVID-relevant materials are incorporated into multiple services: instant library (COVID information), personal stories (how others have prevented or dealt with COVID), risk assessments (evaluate-your-risk simulation), crisis assessments (what to do if infected), warning signs (possible infection or vaccine side effects), healthy/safe/fun things to do together, surveys (adherence to preventive behaviors), and reminders (COVID prevention and vaccine opportunities).

Instant library. Frequently asked questions and brief information on addiction and couples-related issues (e.g. taking care of yourself, financial matters, substance abuse, crisis intervention, referral, medications).

Discussion groups. Forums connect patients or partners with others. Posts are analyzed to predict relapse.

Optional Video Meetings: Regularly scheduled group meetups facilitated by research staff via zoom. Attending video meetings is completely optional and study participants can choose to have their camera on or off, and no one is required to speak. To foster open and honest dialogue, each meeting will be held for each specific group in the study. So, participants in different groups will not be able to attend another group's meeting.

Personal stories. Audio/video of patients and family partners talking about experiences dealing with addiction. The audio/video is not of active study participants, but volunteers willing to share their experiences.

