Intention-to-Treat and Subject Noncompliance. Standard intention-to-treat (ITT) estimates the average treatment effect by comparing outcomes based on assignment of the treatment, but ignoring use of the treatment. Because ITT effect estimates do not represent treatment efficacy under noncompliance (e.g. a drinker is randomized to FamCHESS-C but does not use the system), we will also estimate noncompliance by estimating treatment effects only for compliers, using As-treated, Per-Protocol¹¹⁰ and CACE.¹¹¹

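### As-treated and per-protocol results are labelled effects for compliers, but of the three planned methods only CACE targets that effect

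*Combined protocol and SAP*

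**What the plan says.** Section 8.0, under Intention-to-Treat and Subject Noncompliance, starts from ITT: "Standard intention-to-treat (ITT) estimates the average treatment effect by comparing outcomes based on assignment of the treatment, but ignoring use of the treatment". It says ITT does not show efficacy when people do not comply, and gives the example that "a drinker is randomized to FamCHESS-C but does not use the system". It then adds that "we will also estimate noncompliance by estimating treatment effects only for compliers, using As-treated, Per-Protocol" and CACE. All three methods carry one label. The paragraph does not rank them, define use, adjust for who chooses to use the app, or state the CACE assumptions.

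Section 5.0 supplies the relevant design facts:
- **Control arm:** "Both the drinker and family partner will receive a smartphone with pre-programmed contact information for Alcoholics Anonymous" and other support lines. There is no app.
- **ACHESS-C arm:** both members get a phone, but "only the drinker will receive the ACHESS-C app".
- **FamCHESS-C arm:** drinker and partner both get the app.
- **Use data:** "All uses of the apps are automatically logged to create measures of use of different services".
- **Non-use:** "We will be automatically notified of drinker non-use lasting 2 weeks". This triggers a contact and is not an analysis definition.

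**The concern.** App use is decided after randomization, by the participant. Drinkers who keep using a recovery app may well be those who would have cut down anyway. Control participants have no app, so the would-be users among them cannot be picked out to form a like-for-like comparison. An analysis that selects on use in one arm only therefore sets a more motivated group against an unselected or less motivated one.

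The paragraph tells the reader that ITT is not efficacy and that these analyses fill the gap. If ITT is null, a positive per-protocol or as-treated result would arrive with a pre-specified label saying that the app works for those who use it. With no use definition fixed, who counts as a complier could also be settled after results are seen.

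**Working it through.** **Inputs from the documents.** 198 dyads, 66 per arm, about 180 (60 per arm) at 8 months (section 7.0). Planned effects are d=.40 for ACHESS-C vs control and for FamCHESS-C vs ACHESS-C, and roughly d=.80 for FamCHESS-C vs control (section 8.0, Power). The plan gives no figure for the bias of these analyses, so there is none to reproduce.

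**Assumed, because not given.** Share of users p = .4, .6, .8. Correlation r between engagement and a good outcome = .2 to .5. True app effect zero. Two-sided 5% tests. Positive d favours the app.

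**Step 1: who is compared with whom.**
- ITT: whole app arm vs whole control arm.
- Per-protocol (PP): app-arm users vs whole control arm; app-arm non-users are dropped.
- As-treated (AT): app-arm users vs controls plus app-arm non-users.
- CACE: the ITT difference divided by p, which is the effect in would-be users if assignment does nothing for non-users.

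**Step 2: one follow-up comparison.** Let engagement be standard normal, with the top share p being users, and let φ be the normal density at the cut-off (.386 at p=.4 or .6; .280 at p=.8). With no app effect, users average rφ/p, non-users −rφ/(1−p) and controls 0. Then
- PP bias = rφ/p
- AT bias = rφ/p + rφ/(2−p), because the comparison group averages −rφ/(2−p).

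Example, p=.6 and r=.2: PP = .2×.386/.6 = .129; AT = .129 + .2×.386/1.4 = .184.

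| Use | PP spurious d (rejection) | AT spurious d (rejection) |
|---|---|---|
| 40% | .19–.48 (13–58%) | .24–.60 (19–82%) |
| 60% | .13–.32 (10–36%) | .18–.46 (16–70%) |
| 80% | .07–.18 (6–16%) | .12–.29 (9–37%) |

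Ranges run from r=.2 to r=.5. Rejection rates are simulated at 66 per arm; repeat runs differ by up to about two percentage points.

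**Step 3: the same in plainer units.** The outcome gap between would-be users and non-users is rφ/[p(1−p)]. At 60% use, r=.2 is a gap of .2×.386/.24 = .32 SD and r=.5 a gap of .80 SD. In terms of the gap, PP bias = (1−p)×gap and AT bias = [2(1−p)/(2−p)]×gap. A spurious d of .40 at 60% use therefore needs a gap of .40×1.4/.8 = .70 SD for AT and .40/.4 = 1.00 SD for PP. The largest value in the table is .60, below the .80 planned for FamCHESS-C vs control.

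**Step 4: arm by time.** The plan tests treatment-by-time contrasts in mixed models. Take change scores with an assumed baseline–follow-up correlation of .5, so the SD of change is √[2(1−.5)] = 1. Engagement then correlates with change by r(follow-up) − r(baseline), and this replaces r in Step 2.
- Equal correlations: bias about 0, rejection about 5%.
- Baseline correlation half the follow-up one: bias about half the table's values.
- Engagement related to follow-up only: essentially the table's values.

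Simulation at 60 per arm agrees with all three.

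**Step 5: ITT and CACE under the same null.** ITT averages 0 and rejects about 5% of the time. CACE = ITT/p averages −0.02 to 0.00 in simulation.

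**Step 6: a limit of CACE.** If users are defined by a threshold, and a share q of the app arm use the app less than that but gain e, then ITT = pτ + qe, where τ is the effect in users above the threshold. CACE becomes τ + qe/p. It is biased unless e = 0.

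**The case against.** The strongest reply is that the plan's models look at change over time. If engaged drinkers differ equally at baseline and follow-up, the difference cancels and both methods reject at about the nominal 5%. That is right, and it means the table in Step 2 cannot be read straight across to the planned analysis. It does not remove the problem: engagement that tracks motivation may well predict change, and nothing in the plan rules that out.

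The analyses are also additional to ITT, CACE is already among them, and no passage says they will override ITT or support an efficacy claim. This stands, and it limits the point to the labelling and interpretation of secondary results.

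Low use cannot be presumed either, since the plan contacts drinkers after two weeks of non-use and the apps send prompts. At 80% use the spurious effects are much smaller.

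A reader might infer that both methods set users against everyone else. That is true of as-treated only; per-protocol drops app-arm non-users and its bias is smaller. A reader might also infer that CACE is planned for FamCHESS-C vs ACHESS-C. The paragraph does not say so, and app use in those two arms is handled separately by mediation models.

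**Conclusion.** The point holds as one of labelling and estimand. With self-selected use and no app in the control arm, as-treated and per-protocol do not estimate an effect in compliers. This follows from the design and needs no outside figure.

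The size is conditional. Under a true null, with 40–80% use and r of .2–.5, a single follow-up comparison gives a spurious d of about .07–.48 for per-protocol (rejecting about 6–58%) and .12–.60 for as-treated (about 9–82%). In an arm-by-time analysis it lies between about zero and roughly those values.

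It is tempting to conclude that these analyses would show an effect near the planned size when none exists. The documents do not support that as a general statement. It needs low use or strong selection that also predicts change, and the benchmark would be d=.40 only; no case tried reaches .80. The practical risk is a biased secondary result that already carries an efficacy label, mainly after a null ITT.

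**What to change.** 1. Keep ITT as the main analysis.
2. Make CACE the only analysis called a complier effect, for FamCHESS-C vs control and ACHESS-C vs control, where noncompliance is one-sided.
3. Before unblinding, fix the use definition from the logged data: any use or a threshold, and whether drinker or dyad use counts.
4. State the exclusion restriction, and note that a threshold above any use biases CACE if lighter use has an effect.
5. Drop as-treated and per-protocol, or report them as descriptive and not as complier or efficacy estimates.
6. For FamCHESS-C vs ACHESS-C, where drinkers in both arms have an app, report ITT only, unless the extra assumptions for a complier analysis are written down.

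The cost is SAP wording and giving up the efficacy reading of two commonly reported analyses. No new data, participants or procedures are needed.
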